7.5.2. Supportive Care Guidelines for Pembrolizumab

Patients should receive appropriate supportive care measures as deemed necessary by the treating investigator. Suggested supportive care measures for the management of AEs with potential immunologic etiology are outlined below. Where appropriate, these guidelines include the use of oral or IV treatment with corticosteroids as well as additional anti-inflammatory agents if symptoms do not improve with administration of corticosteroids. Note that several courses of steroid tapering may be necessary, as symptoms may worsen when the steroid dose is decreased. For each disorder, attempts should be made to rule out other causes, such as metastatic disease or bacterial or viral infection, which might require additional supportive care. The treatment guidelines are intended to be applied when the investigator determines the events to be related to pembrolizumab.

Note: If after the evaluation the event is determined not to be related, the investigator does not need to follow the treatment guidance (as outlined below). Refer to Section [7.2.4](#) for dose modification guidelines.

It may be necessary to perform conditional procedures such as bronchoscopy, endoscopy, or skin photography as part of evaluation of the event.

7.5.2.1. Pneumonitis

Grade 2 immune-mediated pneumonitis events should be treated with systemic corticosteroids. When symptoms improve to Grade 1 or less, steroid taper should be started and continued over no less than 4 weeks.

Pembrolizumab should be permanently discontinued in patients who experience recurrent Grade 2 pneumonitis.

Grade 3 or 4 events should be immediately treated with IV steroids. Administer additional anti-inflammatory measures, as needed.

Prophylactic antibiotics for opportunistic infections should be added in the case of prolonged steroid administration.

7.5.2.2. Diarrhea/Colitis

Subjects should be carefully monitored for signs and symptoms of enterocolitis (such as diarrhea, abdominal pain, blood or mucus in stool, with or without fever) and of bowel perforation (such as peritoneal signs and ileus).

All patients who experience diarrhea/colitis should be advised to drink liberal quantities of clear fluids. If sufficient oral fluid intake is not feasible, fluid and electrolytes should be substituted via IV infusion. For Grade 2 or higher diarrhea, consider GI consultation and endoscopy to confirm or rule out colitis.

For **Grade 2 diarrhea/colitis**, administer oral corticosteroids.

For **Grade 3 or 4 diarrhea/colitis**, treat with IV steroids followed by high-dose oral steroids.

When symptoms improve to Grade 1 or less, steroid taper should be started and continued over no less than 4 weeks.

7.5.2.3. Type 1 Diabetes Mellitus or Hyperglycemia

The following are recommendations for management of Type 1 diabetes mellitus (if new onset, including diabetic ketoacidosis [DKA]) or Grade ≥ 3 hyperglycemia, if associated with ketosis (ketonuria) or metabolic acidosis (DKA):

- Insulin replacement therapy is recommended for Type 1 diabetes mellitus and for Grade 3 or 4 hyperglycemia associated with metabolic acidosis or ketonuria.
- Evaluate patients with serum glucose and a metabolic panel, urine ketones, glycosylated hemoglobin, and C-peptide.

Grade 2 events should be treated with corticosteroids. When symptoms improve to Grade 1 or less, steroid taper should be started and continued over no less than 4 weeks. Replacement of appropriate hormones may be required as the steroid dose is tapered.

Grade 3 or 4 events should be treated with an initial dose of IV corticosteroids followed by oral corticosteroids. When symptoms improve to Grade 1 or less, steroid taper should be started and continued over at least 4 weeks. Replacement of appropriate hormones may be required as the steroid dose is tapered.

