7.2.4.2. Pembrolizumab

Adverse events (both nonserious and serious) associated with pembrolizumab exposure may represent an immunologic etiology. These immune-related AEs (irAEs) may occur shortly after the first dose or several months after the last dose of treatment and may affect more than one body system simultaneously. Therefore, early recognition and initiation of treatment is critical to reduce complications. Based on existing clinical study data, most irAEs were reversible and could be managed with interruptions of pembrolizumab, administration of corticosteroids and/or other supportive care. For suspected irAEs, ensure adequate evaluation to confirm etiology or exclude other causes. Additional procedures or tests such as bronchoscopy, endoscopy, and/or skin biopsy may be included as part of the evaluation. Based on the severity of irAEs, withhold or permanently discontinue pembrolizumab and administer corticosteroids. Dose modification and toxicity management guidelines for irAEs associated with pembrolizumab are provided in [Table JGDQ.4](#). See [Section 7.5.2](#) for supportive care guidelines for pembrolizumab, including use of corticosteroids.

Table JGDQ.4. Dose Modification and Toxicity Management Guidelines for Immune-Related AEs Associated with Pembrolizumab

General instructions:
 
Corticosteroid taper should be initiated upon AE improving to Grade 1 or less and continue to taper over at least 4 weeks.
 
For situations where pembrolizumab has been withheld, pembrolizumab can be resumed after AE has been reduced to Grade 1 or 0 and corticosteroid has been tapered. Pembrolizumab should be permanently discontinued if AE does not resolve within 12 weeks of last dose or corticosteroids cannot be reduced to ≤ 10 mg prednisone or equivalent per day within 12 weeks.
 
For severe and life-threatening irAEs, IV corticosteroid should be initiated first followed by oral steroid. Other immunosuppressive treatment should be initiated if irAEs cannot be controlled by corticosteroids.
				
Immune-related AEs	Toxicity grade or conditions (CTCAEv4.0)	Action taken to pembrolizumab	irAE management with corticosteroid and/or other therapies	Monitor and follow-up

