Pneumonitis	Grade 2	Withhold	Administer corticosteroids (initial dose of 1-2 mg/kg prednisone or equivalent) followed by taper	
Monitor participants for signs and symptoms of pneumonitis
 
Evaluate participants with suspected pneumonitis with radiographic imaging and initiate corticosteroid treatment
 
Add prophylactic antibiotics for opportunistic infections

	Grade 3 or 4, or recurrent Grade 2	Permanently discontinue		
Diarrhea / Colitis	Grade 2 or 3	Withhold	Administer corticosteroids (initial dose of 1-2 mg/kg prednisone or equivalent) followed by taper	
Monitor participants for signs and symptoms of enterocolitis (ie, diarrhea, abdominal pain, blood or mucus in stool with or without fever) and of bowel perforation (ie, peritoneal signs and ileus). Participants with \geq Grade 2 diarrhea suspecting colitis should consider GI consultation and performing endoscopy to rule out colitis.
 
Participants with diarrhea/colitis should be advised to drink liberal quantities of clear fluids. If sufficient oral fluid intake is not feasible, fluid and electrolytes should be substituted via IV infusion.

	Grade 4	Permanently discontinue		
AST / ALT elevation or Increased	Grade 2	Withhold	Administer corticosteroids (initial dose of 0.5- 1 mg/kg prednisone or equivalent) followed by taper	Monitor with liver function tests (consider weekly or more frequently until liver enzyme value returned to baseline or is stable)

bilirubin	Grade 3 or 4	Permanently discontinue	Administer corticosteroids (initial dose of 1-2 mg/kg prednisone or equivalent) followed by taper	
Type 1 diabetes mellitus (T1DM) or Hyperglycemia	Newly onset T1DM or Grade 3 or 4 hyperglycemia associated with evidence of β -cell failure	Withhold	Initiate insulin replacement therapy for participants with T1DM Administer anti-hyperglycemic in participants with hyperglycemia	Monitor participants for hyperglycemia or other signs and symptoms of diabetes.
Hypophysitis	Grade 2	Withhold	Administer corticosteroids and initiate hormonal replacements as clinically indicated.	Monitor for signs and symptoms of hypophysitis (including hypopituitarism and adrenal insufficiency)
	Grade 3 or 4	Withhold or permanently discontinue ¹		
Hyperthyroidism	Grade 2	Continue	Treat with non-selective beta-blockers (e.g., propranolol) or thionamides as appropriate	Monitor for signs and symptoms of thyroid disorders.
	Grade 3 or 4	Withhold or permanently discontinue ¹		

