7.5.2.5. Hyperthyroidism or Hypothyroidism

Thyroid disorders can occur at any time during treatment. Patients should be monitored for changes in thyroid function (at the start of treatment, periodically during treatment, and as indicated based on clinical evaluation) and for clinical signs and symptoms of thyroid disorders.

Grade 2 hyperthyroidism events (and **Grade 2 to 4** hypothyroidism):

- In hyperthyroidism, non-selective beta-blockers (for example, propranolol) are suggested as initial therapy.
- In hypothyroidism, thyroid hormone replacement therapy with levothyroxine or liothyronine is indicated per standard of care.

Grade 3 or 4 hyperthyroidism:

- Treat with an initial dose of IV corticosteroid followed by oral corticosteroids. When symptoms improve to Grade 1 or less, steroid taper should be started and continued over no less than 4 weeks. Replacement of appropriate hormones may be required as the steroid dose is tapered.

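### In Phase 1a, Table JGDQ.3 permits a second olaratumab reduction for a recurrence that section 7.2.4.1 says ends treatment; separately, the Grade 2 corticosteroid sentence in 7.5.2.3 is not limited to that section's scope

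*Protocol*

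**What the plan says.** **Olaratumab, Phase 1a.** Four places in the protocol bear on this.

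- Section 7.2.2.2 counts a possibly related nonhematologic toxicity of Grade 3 or higher in Cycle 1 as a DLT, unless a listed exception applies. An event that meets the same criteria in a later cycle, in a Phase 1a patient, is a DLET.
- Section 7.2.4.1 allows up to two olaratumab reductions in general. It then says that a patient with a DLET at a reduced dose level is to be taken off *study treatment*. The sentence just before it, on patients who need more than two reductions, speaks of olaratumab only.
- Table JGDQ.3 (section 7.2.4.1.2), Grade 3 row, covers olaratumab-related toxicity not adequately controlled by supportive care. It gives a first reduction to 12 mg/kg (15-mg/kg cohort, marked as Phase 1a) or 15 mg/kg (20-mg/kg cohort). If toxicity returns after dosing resumes, it permits a second, to 10 or 12 mg/kg. The Grade 4 row stops all study treatment when Grade 4 toxicity recurs.
- Section 6.3.2 lets a patient who must stop one drug for safety stay on the other at the investigator's discretion.

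**Diabetes and hyperglycemia on pembrolizumab.** The lead-in of section 7.5.2.3 covers new-onset type 1 diabetes mellitus (T1DM), with no grade stated. It also covers hyperglycemia of Grade 3 or higher with ketosis or metabolic acidosis. The section later says "Grade 2 events should be treated with corticosteroids" and asks for a taper of at least 4 weeks. The matching row of Table JGDQ.4 has the condition "Newly onset T1DM or Grade 3 or 4 hyperglycemia associated with evidence of" beta-cell failure. Its management cell reads "Initiate insulin replacement therapy for participants with T1DM" and adds anti-hyperglycemics for hyperglycemia; it lists no corticosteroid. The table's general instructions say "For severe and life-threatening irAEs, IV corticosteroid should be initiated first followed by oral steroid", and section 7.2.4.2 refers readers to 7.5.2 "for supportive care guidelines for pembrolizumab, including use of corticosteroids".

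**The concern.** For one type of Phase 1a event the protocol gives two instructions, and no text ranks them. A site working from Table JGDQ.3 could re-dose a patient whom section 7.2.4.1 requires to stop. A site working from 7.2.4.1 would stop, but could not tell whether pembrolizumab must stop too. Patients with the same event could then be managed differently at different sites, in the part of the study whose purpose is to establish tolerability.

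The second matter is smaller. The Grade 2 sentence in 7.5.2.3 stands alone, so it can be read as reaching Grade 2 hyperglycemia, which neither the section's lead-in nor the table row covers. For new-onset T1DM, which both cover, a site using the section would consider steroids while a site using the table row would find only insulin.

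**Working it through.** The plan states no figure on this point, so the check is a comparison of texts with simple dose arithmetic.

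**Step 1. When a recurrence is a DLET (7.2.2.2).** All of these must hold: Phase 1a patient; any cycle other than Cycle 1; possibly related; nonhematologic, Grade 3 or higher; no DLT exception applies.

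**Step 2. The two rules applied to one patient.** Take a Phase 1a patient in the 15-mg/kg cohort. A Grade 3 olaratumab-related nonhematologic toxicity leads to 12 mg/kg. The same toxicity returns at Grade 3 in a later cycle, with no exception.

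- Table JGDQ.3, Grade 3 row: a second reduction, to 10 mg/kg, is permitted.
- Section 7.2.4.1: this is a DLET at a reduced dose, so the patient stops.

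The 20-mg/kg cohort gives the same result (20, then 15, then 12 mg/kg, against stopping).

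**Step 3. Where the rules do not collide.**

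- Recurrence below Grade 3, or under a DLT exception: not a DLET.
- Recurrence still within Cycle 1: not a DLET.
- Recurrent Grade 4 toxicity: the Grade 4 row also stops treatment.
- Phase 1b: a DLET is defined for Phase 1a patients only.

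**Step 4. Size of the difference.** Olaratumab is given on Days 1 and 8, so the dose per 21-day cycle is 2 × the dose level.

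- 15-mg/kg cohort: 2 × 10 = 20 mg/kg after a second reduction, against 2 × 15 = 30 mg/kg at the start; 20/30 = 67%.
- 20-mg/kg cohort: 2 × 12 = 24 mg/kg, against 2 × 20 = 40 mg/kg; 24/40 = 60%.
- Under 7.2.4.1: 0 in either cohort.

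The population at risk is Phase 1a, up to approximately 12 patients (section 10.1.1), and among them only those already on a reduced dose.

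**Step 5. Which drugs stop.** The DLET sentence says *study treatment*, the sentence before it names olaratumab, and the Grade 4 row says all study treatment. The change of term hints at both drugs. Section 6.3.2 leaves room for pembrolizumab alone. The text does not settle it.

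**Step 6. Section 7.5.2.3 against Table JGDQ.4.**

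| Event | Lead-in of 7.5.2.3 | T1DM row of Table JGDQ.4 | Steroid in 7.5.2.3 | Steroid in the row |
|---|---|---|---|---|
| Grade 2 hyperglycemia | outside | outside | yes, if the Grade 2 sentence is read without limit | none |
| New-onset T1DM, any grade | inside | inside | yes, at Grade 2 and at Grade 3 or 4 | none |
| Grade 3 or 4 hyperglycemia | inside, with ketosis or acidosis | inside, with evidence of beta-cell failure | yes | none |

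The suggested taper is at least 4 weeks, that is 4 × 7 = 28 days.

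**The case against.** **On olaratumab.** Table JGDQ.3 is presented as general guidance and only permits the second reduction. Section 7.2.4.1 is specific and mandatory. On ordinary reading the specific rule governs, and a site that stops treatment breaches neither text. The Grade 3 row also still has uses: recurrences that are not DLETs, and all of Phase 1b. Naming the Phase 1a cohort therefore does not by itself prove a conflict. This has force and keeps the point small. It does not remove it, because no sentence states the precedence, 7.2.4.1 itself allows two reductions in general, and a site looking up the table sees no exception.

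**On 7.5.2.3.** A reader might infer that every Grade 2 event lies outside the section's scope. The documents do not support that: T1DM carries no grade limit in the lead-in or in the table row, and in a section so scoped the Grade 2 sentence can be read as meaning T1DM. Only Grade 2 hyperglycemia is outside.

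A reader might also take the table row's silence as proof that steroids are wrong. The cross-reference in 7.2.4.2 sends readers to 7.5.2 for corticosteroid use without limiting the grade, so silence in the row cannot be decisive. At Grade 3 or 4, the table's general instruction for severe events supports steroids. Section 7.5.2.5 follows the same pattern for Grade 3 or 4 hyperthyroidism ("Treat with an initial dose of IV corticosteroid followed by oral corticosteroids"), although that table row lists only beta-blockers or thionamides.

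Finally, 28 days might be read as a required steroid exposure. Section 7.5.2 describes its measures as suggestions, for use as the investigator finds necessary and when the event is judged related to pembrolizumab; 7.5.2.3 calls its own content recommendations. What remains is an unlimited sentence and a mismatch between section and table that clinicians should resolve.

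**Conclusion.** The main point stands as an error of wording. For a Phase 1a DLET that is a Grade 3 recurrence on a reduced olaratumab dose, Table JGDQ.3 permits re-dosing and section 7.2.4.1 requires stopping. At stake is 20 or 24 mg/kg per cycle against none, in a subset of up to approximately 12 patients. The documents give no rate for such recurrences, so no frequency is estimated. The conclusion rests on reading the DLT and DLET definitions as written.

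The secondary point stands in a limited form. The Grade 2 steroid sentence is not confined to the section's scope, and the T1DM row lists no steroid at any grade. Whether new-onset T1DM should receive corticosteroids is a clinical question that the documents leave open; this review does not claim that the steroid text is clinically wrong.

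Severity is minor. No sample size, estimate or escalation rule changes.

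**What to change.** 1. In the Grade 3 row of Table JGDQ.3, add that the second reduction does not apply to a Phase 1a DLET at a reduced dose, for which section 7.2.4.1 governs.
2. In the DLET sentence of 7.2.4.1, replace *study treatment* with either *olaratumab* or *both study drugs*, so that it can be read alongside section 6.3.2.
3. In 7.5.2.3, limit the Grade 2 sentence so that it does not apply to Grade 2 hyperglycemia. Do not simply delete the paragraph: that would also decide the question for Grade 2 new-onset T1DM, which is within scope.
4. Have the sponsor's clinicians align 7.5.2.3 and the T1DM row of Table JGDQ.4 on whether corticosteroids apply to new-onset T1DM and to Grade 3 or 4 hyperglycemia.

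The cost is amendment wording for the named sentences and a notice to sites, with a short clinical decision for item 4. Sample size, visit schedule and data collection are untouched.

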7.5.2.4. Hypophysitis

For Grade 2 events, treat with corticosteroids. When symptoms improve to Grade 1 or less, steroid taper should be started and continued over no less than 4 weeks. Replacement of appropriate hormones may be required as the steroid dose is tapered.

For Grade 3 to 4 events, treat with an initial dose of IV corticosteroids followed by oral corticosteroids. When symptoms improve to Grade 1 or less, steroid taper should be started and continued over no less than 4 weeks. Replacement of appropriate hormones may be required as the steroid dose is tapered.

7.5.2.5. Hyperthyroidism or Hypothyroidism

Thyroid disorders can occur at any time during treatment. Patients should be monitored for changes in thyroid function (at the start of treatment, periodically during treatment, and as indicated based on clinical evaluation) and for clinical signs and symptoms of thyroid disorders.

Grade 2 hyperthyroidism events (and **Grade 2 to 4** hypothyroidism):

- In hyperthyroidism, non-selective beta-blockers (for example, propranolol) are suggested as initial therapy.
- In hypothyroidism, thyroid hormone replacement therapy with levothyroxine or liothyronine is indicated per standard of care.

Grade 3 or 4 hyperthyroidism:

- Treat with an initial dose of IV corticosteroid followed by oral corticosteroids. When symptoms improve to Grade 1 or less, steroid taper should be started and continued over no less than 4 weeks. Replacement of appropriate hormones may be required as the steroid dose is tapered.

7.5.2.6. Hepatic Injury

For **Grade 2** immune-mediated hepatitis, monitor liver function tests more frequently until returned to baseline values (consider weekly). Treatment with IV or oral corticosteroids should be considered.

For **Grade 3 or 4** immune-mediated hepatitis, treat with IV corticosteroids for 24 to 48 hours.

When symptoms improve to Grade 1 or less, a steroid taper should be started and continued over no less than 4 weeks.

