7.2.1.2. Pembrolizumab

Pembrolizumab will be administered as a 200-mg fixed dose intravenously over 30 minutes on Day 1 of a 21-day cycle. Every effort should be made to ensure infusion timing is as close as possible to 30 minutes. However, a window of between -5 minutes and +10 minutes is permitted (that is, infusion time is 30 minutes -5 min/+10 min). Patients should be monitored in Cycles 1 and 2 for signs and symptoms of IRRs for 3 hours following the end of the pembrolizumab infusion.

Table JGDQ.2. Phase 1a and 1b Study Drug Administration

Drug	Dose Level	Dose	Route	Dosing Day of 21-Day Dosing Period
olaratumab	Level 1	15 mg/kg	IV	Day 1 and Day 8
	Level 2	20 mg/kg	IV	Day 1 and Day 8
pembrolizumab	Fixed dose	200 mg	IV	Day 1

Abbreviations: IV = intravenous.

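### For Grade 2 immune-mediated liver events, Table JGDQ.4 directs corticosteroids while Section 7.5.2.6 leaves them optional, and no text says which governs

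*Protocol*

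**What the plan says.** Two places in the protocol deal with a Grade 2 liver event attributed to pembrolizumab.

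- Section 7.2.4.2, Table JGDQ.4, row for AST/ALT elevation or increased bilirubin, Grade 2: the action is to withhold pembrolizumab, and the management column reads "Administer corticosteroids (initial dose of 0.5- 1 mg/kg prednisone or equivalent) followed by taper".
- Section 7.5.2.6, Grade 2 immune-mediated hepatitis: liver tests are to be done more often, and "Treatment with IV or oral corticosteroids should be considered".

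The general instructions at the head of Table JGDQ.4 set the timing: "Corticosteroid taper should be initiated upon AE improving to Grade 1 or less and continue to taper over at least 4 weeks". Section 7.5.2.6 gives the same minimum: "a steroid taper should be started and continued over no less than 4 weeks". On restarting after a hold, the general instructions say that "pembrolizumab can be resumed after AE has been reduced to Grade 1 or 0 and corticosteroid has been tapered". They also require permanent discontinuation if "corticosteroids cannot be reduced to ≤ 10 mg prednisone or equivalent per day within 12 weeks".

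The two sections refer to each other. Section 7.2.4.2 sends the reader to Section 7.5.2 for corticosteroid use. Section 7.5.2 presents its measures as suggestions and sends the reader back to Section 7.2.4 for dose modification. Neither says which text prevails where they differ.

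**The concern.** One text directs steroids and the other leaves them to judgement. The row and the section carry different labels, but the table covers immune-related events associated with pembrolizumab and Section 7.5.2 covers events judged related to it, so an immune-mediated Grade 2 liver event falls under both.

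The difference matters because steroid use is tied to the restart rule. A patient given steroids must satisfy the tapering condition before pembrolizumab resumes and becomes subject to the discontinuation rule for steroids that cannot be reduced. A patient not given steroids meets neither. The same event can therefore lead to different steroid exposure and a different length of interruption, depending on which page the site follows.

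Safety and tolerability is the primary objective of both phases. AEs leading to dose adjustments (protocol Section 10.4) and omissions, cycle delays and percent dose intensity (SAP Section 6.13.1) are planned summaries. In a study of about 37 patients, a few events handled differently can change how those summaries read.

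**Working it through.** The plan states no figure to reproduce, so this is a day count from its own rules.

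Inputs from the documents:
- Minimum taper: 4 weeks = 28 days, starting at Grade 1 or less (Table JGDQ.4 general instructions; Section 7.5.2.6 agrees).
- Dosing: "Pembrolizumab will be administered as a 200-mg fixed dose intravenously over 30 minutes on Day 1 of a 21-day cycle" (Section 7.2.1.2). Counting the last dose given as Day 1, the next are due on Days 22, 43 and 64.
- Visit window: 3 days either side (Attachment 1, footnote d), so the Day 22 dose may be given up to Day 25.

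Inputs assumed, because the documents give neither: onset day *d* from 1 to 21, and time *r* from onset to Grade 1 or less from 0 to 21 days.

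Formulas, reading the tapering condition as a completed taper:
- With steroids, earliest restart = *d* + *r* + 28.
- Without steroids (inferred reading), earliest restart = *d* + *r*.
- Delay = restart day − 22, or 0 if negative.

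**Smallest possible interruption with steroids.** With *d* = 1 and *r* = 0, restart is 1 + 0 + 28 = Day 29. That is 29 − 22 = 7 days after the due date and 29 − 25 = 4 days past the window. Any later onset or slower recovery only adds to this, so on this reading at least one scheduled dose is always late or omitted.

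**Examples across the assumed range.**

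| Onset *d* | Recovery *r* | With steroids: restart (delay) | Without steroids: restart (delay) |
|---|---|---|---|
| 1 | 0 | Day 29 (7 days) | Day 1 (0) |
| 8 | 7 | Day 43 (21 days) | Day 15 (0) |
| 15 | 14 | Day 57 (35 days) | Day 29 (7 days) |
| 21 | 21 | Day 70 (48 days) | Day 42 (20 days) |

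The hold from onset is *r* + 28, or 28 to 49 days, with steroids and *r*, or 0 to 21 days, without. With steroids, between one and three of the original dosing dates pass. Without them at most one does, since the latest restart, Day 42, is past Day 25 but not past 43 + 3 = Day 46.

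**Sensitivity to the tapering condition.** The instructions do not define it. Suppose that reaching 10 mg/day, the level used in the discontinuation rule, were enough. Assume a linear 28-day taper from starting dose *s* and body weights of 50 to 100 kg. The time to 10 mg/day is 28 × (*s* − 10)/*s*:
- 50 kg at 0.5 mg/kg: *s* = 25 mg, 28 × 15/25 = 16.8 days.
- 100 kg at 1 mg/kg: *s* = 100 mg, 28 × 90/100 = 25.2 days.

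With *d* = 1 and *r* = 0, the first case allows restart at about Day 18, before the Day 22 dose; the second at about Day 26, just past the window. The two paths still differ by about 17 to 25 days in the earliest restart, but a dose is no longer always affected.

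**The case against.** The strongest defence is that the texts can be read together. Section 7.5.2 offers suggestions for the investigator's judgement and defers to Section 7.2.4 for dose modification. Section 7.2.4.2 presents the table as covering toxicity management as well as dosing, and its own text calls for corticosteroids according to severity. A site that follows the table breaches nothing in Section 7.5.2.6.

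That is true in one direction only. A site that considers steroids under Section 7.5.2.6 and decides against them departs from the table. Section 7.2.4.2 itself sends sites to Section 7.5.2 for steroid use, and the table too is titled as guidelines. Loose drafting does not explain the difference either: for Grade 2 pneumonitis, colitis and hypophysitis, Section 7.5.2 calls for steroids, and for nephritis it recommends them. Among these, the hepatic text alone stops at consideration.

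Other parts of the defence do stand. A reader might infer that the protocol prescribes a hold of at least 4 weeks at one site and none at another. It does not. The 28 days depends on reading the tapering condition as a completed taper, and no restart rule is written for a patient never given steroids, so immediate eligibility is an inference. A reader might also infer that a dose is necessarily missed. The delay can be as short as 7 days, and the SAP reports cycle delays separately from omissions. Finally, differing practice would be partly visible: the SAP lists concomitant medications with the associated AE (Section 6.10) and gives reasons for dose adjustments (Section 6.13.1).

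**Conclusion.** The point holds as an internal inconsistency that should be corrected. The two instructions differ, no precedence is stated, and the difference carries through to restarting pembrolizumab. If steroids are given and the taper must be complete, the earliest restart is 28 days after Grade 1 or less. If they are not given, dosing apparently may restart at Grade 1 or less, and an event that gets there before the next Day 1 causes no delay.

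Two larger conclusions are not supported. A reader might infer that dose escalation is compromised. A Grade 2 event does not meet the Grade 3 or higher nonhematologic criterion in Section 7.2.2.2, so the usual escalation decisions are not affected. A reader might also try to state what share of events would go without steroids. That depends on how many sites follow each text and how often those following Section 7.5.2.6 would still give steroids; the documents give neither. They also give no frequency for Grade 2 immune-mediated liver events, so the effect on the trial's summaries of steroid exposure, delays, omissions and dose intensity cannot be sized.

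**What to change.** Reconcile Section 7.5.2.6 with the Grade 2 AST/ALT and bilirubin row of Table JGDQ.4 so that one instruction governs, and add a sentence stating which text prevails wherever Section 7.5.2 and the table differ. In the same edit, state what the tapering condition for restarting means and how restarting works for a patient who received no steroids. What the instruction should be is for the sponsor's medical team. The cost is amendment wording only; no change to sample size, data collection or analysis is needed.
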